#### **10.2** Prior and Concomitant Medications and Therapies

All medications recorded on the Concomitant Medications CRF page will be coded using the World Health Organization drug dictionary (WHODRUG), March 2013 version. Medications will be listed and summarized by Anatomical Therapeutic Chemical (ATC) Level 1 and Preferred Name.

Prior medications are defined as those which are only taken prior to the beginning of the active treatment period. Concomitant medications are medications taken at any time during the active treatment period, or those which are able to be taken during that period. Any medications recorded which begin after the last dose of randomized study treatment will also be classified as concomitant medications. As needed (*PRN*) medications, which may not be taken for long periods of time but which are prescribed to the subject, and the prescription period overlaps with the active treatment period, will be considered concomitant medications.

All non-study medications will be listed by subject. Rescue medications and medications prescribed as a result of an anaphylactic reaction will be listed by subject. Further presentation of epinephrine use data is described in Section 11.1.

Concomitant medications will be summarized by treatment group and overall. Subjects will be counted no more than one time per Preferred Name and no more than 1 time per ATC Level 1 in the summary. A similar summary will be presented for concomitant medications marked as rescue medications.

Concomitant non-drug therapies will be similarly listed by subject.

## **10.3** Adverse Events

All reported adverse events (AEs) will be classified into System Organ Class (SOC) and Preferred Term (PT) using Medical Dictionary for Regulatory Activities (MedDRA) version 16.0. A summary of SOC, PT, and verbatim term will be provided.

Treatment-emergent adverse events (TEAEs) are defined as any event starting during or after the active treatment period. Any event occurring on the same day as a DBPCFC or in-clinic escalation dosing will be considered to be associated with those events, and flagged as such in the listings. Events will be classified by onset time with regards to time of last dose (within 2 hours of last dose, > 2 hours since last dose, and unknown time since last dose).

Events will be further classified by time period of onset, as follows:

- *Pre-study*: All events beginning prior to first dose of Screening DBPCFC; if times are unavailable, any event prior to the first day of Screening DBPCFC.
- Screening DBPCFC: All events beginning after the first dose of the food challenge during the Screening DBPCFC, and within 24 hours of the last dose of that food challenge and prior to the first dose of randomized treatment. If times are not available, any event starting on the same day as any part of the Screening DBPCFC will be categorized as Screening DBPCFC.
- Pre-treatment: All events beginning more than 24 hours after the last dose of the Screening DBPCFC but before the first dose of randomized treatment. If the two halves of the food challenge are more than 24 hours apart, events that begin more than 24 hours after the end of the first half, but prior to the start of the second half, will be categorized as Pre-treatment. If times are not present, events beginning on any day after the first day of Screening DBPCFC, and before Visit 01 Day 1, excluding any day on which Screening DBPCFC is administered, will be Pre-treatment.
- Visit 01: All events beginning on or after the first dose on Visit 01 Day 1, and within 24 hours of the last dose administered at Visit 01 (Days 1, 2, or 3); if times not present, events beginning on the same date as any day of Visit 01.
- *Up-dosing Visit*: All events beginning on or after the increased dose administered and within 24 hours of that dose; if times not present, events

beginning on the same date as a dose increase. If the same dose level, or a decreased dose level, is administered at a scheduled up-dosing visit, an event within 24 hours of that dose or on that day will be classified as On-treatment, unless there had been a higher dose administered within that 24 hour period or on that day, respectively.

- On-treatment: All other events beginning after the first dose of randomized treatment and prior to the Exit DBPCFC, or within 24 hours of the last dose of randomized study treatment if an Exit DBPCFC is not performed or is >24 hours after the last dose. If times are not available, any event starting during the active treatment period, but not on the same day as Visit 01 or an Up-dosing visit, will be On-treatment.
- *Exit DBPCFC*: All events beginning after the first dose of product was administered during the Exit DBPCFC, and within 24 hours of the last dose of that food challenge. If times are not available, any event starting on the same day as any part of the Exit DBPCFC will be categorized as Exit DBPCFC.
- *Post-Exit DBPCFC*: All events beginning more than 24 hours after the Exit DBPCFC. If the two halves of a food challenge are more than 24 hours apart, events that begin more than 24 hours after the end of the first half, but prior to the start of the second half, will be categorized as Post-Exit DBPCFC.
- Post-treatment: All events beginning >24 hours after the last dose and prior to the Exit DBPCFC if an Exit DBPCFC is performed, or >24 hours after the last dose if an Exit DBPCFC is not performed. If times are not available, all events beginning on or after the day after the last part of the Exit DBPCFC (if performed) or the day after the last dose of randomized treatment (if no Exit DBPCFC performed) will be categorized as Post-treatment. If the two halves of the Exit DBPCFC are more than 24 hours apart, events that begin more than 24 hours after the end of the first half, but prior to the start of the second half, will be categorized as Post-treatment.

Listings will be provided for all adverse events; serious adverse events (SAEs); severe, life-threatening, or fatal adverse events; adverse events leading to death; adverse events leading to permanent withdrawal of study treatment; adverse events related to study treatment; and adverse events occurring within 2 hours of the last dose of randomized study treatment. Listings of both adverse events associated with DBPCFC, and SAEs associated with DBPCFC, will be provided. A separate listing of all adverse events, sorted by time period of onset, will also be provided; and SAEs will be flagged.

An overall summary of frequencies of types of adverse events (TEAEs, SAEs, etc.) will be provided. An additional summary table of all TEAEs by Preferred Term, in order of descending frequency, will also be provided.

Summaries of adverse events by time period, SOC, and PT will be provided for TEAEs, treatment-emergent SAEs, and TEAEs related to study treatment. Subjects will be counted at most one time per time period overall, at most one time per SOC and at most one time per PT for these summaries. Summary tables will be sorted in order of time period (overall, then chronological), descending overall frequency of SOC and PT, with alphabetical sorting for ties. The number of subjects at risk for each time period (i.e., the number of subjects on study at the beginning of each time period) will be used as the denominator. In other words, the number of subjects in the Safety population will be used as the denominator for the Overall, On-treatment, and Post-Treatment time periods, the number of subjects undergoing Visit 01 will be used as the denominator for Visit 01, the number of subjects with 1+ updosing visits will be used as the denominator for Updosing Visit, the number of subjects undergoing the Exit DBPCFC will be used as the denominator for the Exit DBPCFC, Post-Exit DBPCFC time points.

Events related to study treatment are defined as those classified as possibly, probably, or definitely related to study treatment. If relationship is missing, the event will be conservatively be summarized as being related to study treatment.

Event severity is classified as mild, moderate, severe, life-threatening, or death. If severity is missing, a separate category of missing severity will be included in the summary table, and no imputation of severity will be performed.

An additional summary of TEAEs by time period, SOC, and PT will be presented by start time of the adverse event relative to last dose (within 2 hours; > 2 hours; and unknown, where the event start time or time of last dose is unknown). TEAEs will also be summarized by time period SOC, PT, and severity. Subjects will be counted at most one time per SOC and at most one time per PT, at the maximum reported severity. If severity is missing, the subject will be summarized as having the highest possible severity.

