7.1 Definitions for Recording of Safety Events

All safety events observed under this protocol are reported through the data system for the duration of the study. Some safety events arising under certain defined conditions are recorded on specific forms as follows.

- Safety events related to accidental food exposure are recorded on a Food Allergy Episode form and are not reported on an adverse event form unless the event is considered a serious adverse event, as defined below (Section 7.2).
- Any allergic symptoms due to dosing will be recorded directly on the Escalation Dosing form (also referred to as a Study Product Administration form).
- For any event occurring after a subject has signed the informed consent form that meets the definition of anaphylaxis, an Anaphylaxis Episode form will be completed and forwarded to the Coordinating Center within 24 h of its occurrence and/or the sites being notified of the event (see also Section 7.7.2), if the event is associated with any of the following:
 - An emergency room visit;
 - Hospitalization;
 - More than 2 doses of epinephrine being given as treatment for the same episode;
 - Assessment of the anaphylaxis as severe, as defined in Appendix 3.
- If any safety event meets the definition of a serious adverse event (whether or not related to dosing), it will also be recorded on an adverse event (AE)/serious adverse event (SAE) form. Skin prick test and food challenge reactions that occur in the clinic are captured on study specific forms and are not reported on an adverse event form unless the event is considered a serious adverse event, as defined below. All serious adverse events are reported on the AE/SAE form set in addition to the Skin Prick form or an Oral Food Challenge form if the event occurred during one of these procedures. All other safety events that occur throughout the study are reported on the AE/SAE form set.

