7.6 Adverse Events Collection Procedures

Any new event or experience that was not present at Screening, or worsening of an event present at Screening, is considered to be an AE. Unchanged, chronic conditions are not AE's and should not be recorded on the AE page of the CRF. Adverse events will be evaluated from the onset of the event until the time the event is resolved or medically stable, or until 30 days after the subject completes study treatment, whichever comes first.

AEs may be discovered through any of these methods:

- Observing the subject
- Questioning the subject, which should be done in an objective manner
- Receiving an unsolicited complaint from the subject
- Review of medical records/source documents
- Review of home dosing symptom logs (provided to record symptoms between visits

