- 7. Phone calls will occur 1 week after each escalation visit to assess dosing compliance and symptoms. Schematic for symptoms is described in Figure 6-1 and Figure 6-2 of the protocol.
- 8. AEs will be evaluated from the onset until the event is resolved or medically stable, or until 30 days after the subject completes study treatment, whichever comes first.

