## 7.5 Data Derivations and Definitions

The following definitions and derivations will be used throughout this study:

- Study Day is calculated as (assessment date first dose date + 1) for assessments and visits performed on or after the first dose date, and (assessment date – first dose date) for assessments and visits prior to the first dose date.
- Baseline is defined as the last non-missing value prior to the first dose of randomized study treatment.
- Change from baseline is calculated as observed value after the first dose baseline value.
- The active treatment period is defined as the time period beginning with the date and time of the first dose of randomized study product, and ending with the date of the last dose of randomized study product taken prior to Exit DBPCFC.

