#### **10.5** Symptoms During DBPCFC

During each food challenge, the severity of pre-specified symptoms (hives, throat tightness, throat swelling, throat discomfort, hoarseness, laryngeal edema, skin flushing, pruritus, rhinorrhea, sneezing, nasal congestion, cough, wheezing, dyspnea, abnormal pain, abdominal cramping, nausea, vomiting) is rated as none, mild, moderate, severe, or life-threatening at each dose level of each food product. In addition, the presence of dose-limiting symptoms is recorded.

Symptoms at the Screening and Exit DBPCFCs will be listed by subject.

Symptoms will be summarized separately for symptoms during Screening DBPCFC (separately for the Safety and Screening DBPCFC Only populations) and Exit DBPCFC (for the Safety population). Subjects will be counted at most one time per symptom for each summary, at the most severe level recorded for that subject. The maximum dose severity of any symptom, and the presence of any dose limiting symptoms, will also be summarized.

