# **2.3 Study Product Administered After Exit DBPCFC**

In some cases, study product was administered following Exit DBPCFC, to allow subjects to continue to receive product prior to rolling over to the ARC002 study. Subjects remained enrolled in the ARC001 study during this time, and recorded study product in the daily diary.

This post-Exit DBPCFC study product will be excluded from summaries of exposure and compliance, and footnoted as such. Disposition listings reflecting the date of last study treatment will be flagged to indicate where study treatment was taken after Exit DBPCFC.

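### Adverse events from the Exit food challenge and from post-Exit product are pooled into the overall TEAE counts, and no planned table gives a pre-Exit total

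*SAP*

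**What the plan says.** **Definition.** SAP 10.3 counts as a TEAE "any event starting during or after the active treatment period". The definition has no closing point. Under SAP 7.5 the active treatment period is the interval from the first randomized dose, "ending with the date of the last dose of randomized study product taken prior to Exit DBPCFC".

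**Tables.** SAP 10.3 assigns each event to an onset period. These include Exit DBPCFC (first challenge dose to 24 hours after the last), Post-Exit DBPCFC and Post-treatment. TEAEs, treatment-emergent SAEs and related TEAEs are tabulated by period, with an Overall row on the Safety population. A subject counts at most once within each period. Tables 14.3.1.1 (overall summary) and 14.3.1.7 (TEAEs by preferred term) are not described as split by period. Addendum 2.1 adds hypersensitivity tables without saying whether they are.

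**Status of challenge food.** SAP 10.1 states that food given at a DBPCFC is not randomized study treatment, and SAP 5.3 disregards it when assigning subjects to safety groups.

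**Recording.** Under Protocol 7.1, in-clinic challenge reactions "are captured on study specific forms and are not reported on an adverse event form unless the event is considered a serious adverse event". SAP 10.5 tabulates them apart from adverse events: "Symptoms will be summarized separately for symptoms during Screening DBPCFC", and likewise for the Exit DBPCFC. Protocol 7.6 limits adverse event evaluation to resolution or stability, or "until 30 days after the subject completes study treatment, whichever comes first". The footnote to SAP Table 3.5 repeats this limit.

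**Post-Exit product.** Addendum 2.3 reports that in some cases "study product was administered following Exit DBPCFC, to allow subjects to continue to receive product prior to rolling over". It removes that product from the exposure and compliance summaries and does not mention adverse events.

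**The concern.** The overall TEAE and SAE counts are what a reader uses to compare the tolerability of CPNA and placebo dosing. As defined, they also contain events from two other sources.

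- **The Exit challenge.** It gives up to 600 mg of peanut protein to both arms, including placebo subjects who are expected to be still reactive. A resulting adverse event comes from the challenge food and not from the assigned treatment.
- **Product taken after the challenge.** Events on this product count as TEAEs, while the matching exposure is excluded.

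If challenge events fall more often on placebo, they narrow any CPNA excess in the pooled counts. With about 25 subjects per arm, one subject is 1/25 = 4 percentage points, so one or two challenge SAEs would show in the SAE comparison.

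**Working it through.** **1. The plan's own figures.** The documents give no TEAE rate. The only stated figures that bear on this point are the challenge pass rates behind the sample size (Protocol 9.3, SAP 4): 25% placebo and 66.7% CPNA among those challenged, with 22 of 25 challenged per arm.
- Effective rates: 0.25 × 22/25 = 22%, and 0.587 × 25/22 = 66.7%. Both match.
- Power by exact enumeration of two binomials (25 per arm, uncorrected Pearson chi-square, two-sided 0.05): 80.0% for 22% v 58.7%, and 80.2% for 20% v 56.6%. This agrees with the stated 80%, so the planning rates are usable as inputs.

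**2. Where an Exit event goes.** Its onset is after the last pre-Exit dose, hence after the active treatment period (7.5). It is therefore a TEAE (10.3) and counts in Overall. The same holds for an event during post-Exit dosing.

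**3. Which challenge events are recorded as adverse events.** Protocol 7.1 removes reactions that are both in-clinic and non-serious. SAEs and reactions after leaving the clinic remain; the Exit period runs 24 hours past the last challenge dose. No rate is given for either. SAP 10.3 plans listings of both AEs and SAEs associated with a DBPCFC, but it defines association by calendar day. Those listings therefore do not show that non-serious challenge reactions are recorded as AEs.

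**4. Can a pre-Exit incidence be recovered from the period rows?** Let A be the subjects with a TEAE before the Exit challenge and B those with one at or after it. Overall is the number in A or B, so all that follows is

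Overall − B ≤ A ≤ Overall.

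A itself is not tabulated. Adding the Visit 01, Up-dosing and On-treatment rows does not give it, because a subject can be in all three. B is not tabulated cleanly either. An event more than 24 hours after the first half of the Exit challenge and before the second half meets the definitions of both Post-Exit DBPCFC and Post-treatment, and those two periods have different denominators.

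**5. Size of the reacting pool on the planning rates.**
- Placebo failing at or before 300 mg: 22 × 0.75 = 16.5 (66% of 25).
- CPNA: 22 × (1 − 0.667) = 7.3 (29% of 25).
- Ratio 16.5/7.326 = 2.25.

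These are failures at or before 300 mg only. Those who pass (5.5 placebo, 14.7 CPNA) go on to 600 mg and may react there. If a share s of passers in each arm reacts, the pools are 16.5 + 5.5s and 7.3 + 14.7s:

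| s | Placebo | CPNA | Ratio |
|---|---|---|---|
| 0 | 16.5 | 7.3 | 2.25 |
| 0.5 | 19.25 | 14.7 | 1.31 |
| 1 | 22 | 22 | 1.00 |

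Unequal shares could move the ratio either way.

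**6. Effect on the any-TEAE difference (illustration).** Let b be the TEAE rate before the challenge, f the share of the arm failing at or before 300 mg, and r the share of those failures recorded as adverse events. Assuming independence, the overall rate is b + (1 − b) f r. The CPNA-minus-placebo difference therefore falls by

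r × [(1 − b_P) × 0.66 − (1 − b_C) × 0.293].

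Assumed ranges: b_C 80–95%, borrowed from the symptom expectations in Protocol 1.6.1; b_P 20–80%, not in the documents.
- Smallest bracket (b_P = b_C = 0.80): 0.132 − 0.0586 = 0.073.
- Largest bracket (b_P = 0.20, b_C = 0.95): 0.528 − 0.0147 = 0.513.

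| r (assumed) | Fall in difference, percentage points |
|---|---|
| 1% | 0.1 to 0.5 |
| 10% | 0.7 to 5.1 |
| 100% | 7 to 51 |

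The last line would need every failure to be recorded as an adverse event, which Protocol 7.1 rules out. It is shown only as the outer limit of this illustration.

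**The case against.** The strongest defence is that an inclusive TEAE definition with period rows is a legitimate and cautious choice. Exit and Post-Exit events already have their own rows and denominators, related TEAEs have their own table (14.3.1.5), DBPCFC-associated events are listed, and no hypothesis test on adverse events is planned. Most challenge reactions never reach the adverse event form. All of this stands, and it limits the point to how the headline counts are presented. It does not supply a pre-Exit total, as step 4 shows.

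A reader might infer three stronger things that the documents do not support.
- **That the overall comparison is materially biased in favour of CPNA.** The 2.25 ratio describes challenge failures at or before 300 mg, not adverse events, and it leaves out reactions at 600 mg.
- **That events accrue without limit.** Evaluation stops by 30 days after study treatment is completed. That limit is not part of the TEAE definition, however, and completion is unclear for subjects dosed after the Exit DBPCFC.
- **That post-Exit events also inflate placebo, or are all unblinded.** Addendum 2.3 does not say which arm took the product, and active subjects who pass may continue dosing in ARC002, so these events could count against CPNA. Protocol 3.3 unblinds after the DBPCFC, whereas SAP 7.8 unblinds when the subject exits ARC001. Addendum 2.3 says these subjects were still enrolled.

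Ending the TEAE definition at the challenge would also go too far. It would drop challenge SAEs from the overall tables and, if unchallenged subjects kept a 30-day tail, would make follow-up depend on whether a subject tolerated up-dosing.

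**Conclusion.** The point holds as a gap in presentation. By definition, the Overall row and the tables not described as split by period mix treatment-phase events with events from challenge food and from post-Exit product, and the planned rows cannot separate them at subject level. This sits awkwardly with the SAP's own rule that challenge food is not randomized treatment.

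The number of events is unknown and probably small. If 1% of the challenge failures were recorded as adverse events, the any-TEAE difference would move by at most about half a point; at 10%, by roughly 1 to 5 points. Both results rest on the planning pass rates, on assumed pre-challenge TEAE rates and on independence. They also count only failures at or before 300 mg.

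For challenge events an excess in placebo is plausible but not established. For post-Exit product the direction cannot be stated.

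**What to change.** Keep the inclusive TEAE definition and all Exit and Post-Exit rows. Then:

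1. Add an overall row limited to onset from the first randomized dose to before the first Exit DBPCFC dose. For unchallenged subjects, close it at the existing On-treatment limit of 24 hours after the last dose. Put the row in Tables 14.3.1.1 and 14.3.1.7, in the by-period TEAE and SAE tables, and in the hypersensitivity tables of Addendum 2.1.
2. Name that row as the basis for comparing the arms over the treatment phase.
3. Flag adverse events with onset during post-Exit dosing, so that they are handled in line with the exposure exclusion in Addendum 2.3.
4. State in SAP 10.3 that Protocol 7.1 governs which challenge reactions are recorded as adverse events.

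The cost is some SAP wording, one derived flag and one more row per table. The downside is that a late drug-related event with onset after the challenge begins is absent from the new row and appears only in the inclusive total and the Exit or Post-Exit rows. No data are dropped.

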## **3.2 Schedule of Study Assessments**

## 3.2.1 Screening Period

The screening visits (Visit 00) may occur over several days, and will include an initial DBPCFC. The DBPCFC will have both a peanut challenge and a placebo challenge, using up to 100 mg (143 mg cumulative) each of peanut protein and placebo, based on the PRACtical issues in ALLergology Joint United States/European Union Initiative (PRACTALL) dosing regimen, as shown in Table 3.1. At the investigator's discretion, a 1 mg dose may be added at the beginning of the escalation.

Challenge Doses					
	Peanut flour with				
Peanut Protein	50% protein content				
(mg)	(mg)				
3	6				
10	20				
30	60				
100	200				

Table 3.1. PRACTALL Screening DBPCFC Dosing Schedule

A DBPCFC is conducted either as two challenges during a single day visit (with at least 3 hours separating the two halves of the challenge) or over 2 days with the placebo challenge on one day and the peanut challenge on the other day. The food challenges are presented in random order and are performed under double-blind conditions.

Subjects who have dose-limiting symptoms at or before the 100 mg dose of peanut protein will be enrolled into the study. Those who successfully consume a dose of 100 mg of peanut protein during the Screening DBPCFC, without experiencing dose-limiting symptoms, will be considered screen failures and will not be randomized. Any subject who is assessed to have had dose-limiting symptoms to both parts of the Screening DBPCFC (i.e., to placebo [oat flour] as well as peanut flour) will be considered to be a screen failure and will not be randomized.

Subjects who meet eligibility criteria will return for a baseline visit, which may occur over multiple days. See Table 3.5 for the schedule of assessments.

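### SAP 10.3 gives conflicting onset periods for adverse events around the Exit challenge: Post-Exit DBPCFC and Post-treatment both claim events between its halves, and a missing clock time moves later events from one to the other

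*SAP*

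**What the plan says.** SAP 10.3 (Adverse Events) assigns events to periods by time of onset, with date-only fallbacks for most periods when clock times are missing. Three statements matter here.

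- **Post-Exit DBPCFC, between halves.** "If the two halves of a food challenge are more than 24 hours apart", an event starting over 24 h past the end of the first half, but "prior to the start of the second half, will be categorized as Post-Exit DBPCFC".
- **Post-treatment, between halves.** "If the two halves of the Exit DBPCFC are more than 24 hours apart", an event in that same interval, "prior to the start of the second half, will be categorized as Post-treatment".
- **Post-treatment, dates only.** Without times, "all events beginning on or after the day after the last part of the Exit DBPCFC" go to Post-treatment when that challenge was performed. With times, the Post-Exit DBPCFC bullet takes everything that starts more than 24 h after the Exit challenge.

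The same section sets the denominators. For Post-treatment, "the number of subjects in the Safety population will be used as the denominator for the Overall, On-treatment, and Post-Treatment time periods". For the other period, "the number of subjects undergoing the Exit DBPCFC will be used as the denominator for the Exit DBPCFC, Post-Exit DBPCFC time points".

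SAP 3.2.1 allows a challenge to be run in one day "or over 2 days with the placebo challenge on one day and the peanut challenge on the other day". SAP 3.2.3 says the Exit challenge is conducted like the Screening one, so its halves can fall on different days. The SAP addendum of 10 February 2015 adds AE classifications and a Completer population but leaves the onset periods unchanged.

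**The concern.** A by-period safety table needs each event to have one period. Here two explicit rules give two answers, in two situations:

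1. An event in the gap between widely spaced halves of the Exit challenge satisfies both the Post-Exit DBPCFC and the Post-treatment rule.
2. An event after the completed Exit challenge changes period merely because its clock time was not recorded. The SAP expects missing times, since it provides an unknown category for onset relative to last dose.

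Two programmers could each follow the text and produce different tables. The affected outputs are those broken down by period: Tables 14.3.1.2 (all TEAEs), 14.3.1.3 (serious), 14.3.1.4 (by time since last dose), 14.3.1.5 (related) and 14.3.1.6 (by severity), together with the listing sorted by period. With about 25 subjects per arm, one misplaced serious or related event is visible. Addendum section 2.3 adds a wrinkle: some subjects took study product after the Exit challenge, so a date-only event could be labelled Post-treatment while the subject was still dosing.

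**Working it through.** The plan gives no figure to reproduce. The check compares the rules and then applies them to example onset times.

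**Step 1. Between-halves rules side by side**

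| | Post-Exit DBPCFC bullet | Post-treatment bullet |
|---|---|---|
| Condition | halves > 24 h apart | halves > 24 h apart |
| Onset after | end of first half + 24 h | end of first half + 24 h |
| Onset before | start of second half | start of second half |
| Assigned period | Post-Exit DBPCFC | Post-treatment |
| Denominator | subjects undergoing the Exit challenge | Safety population |

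Condition and interval are identical; only the assignment differs. The second assignment also contradicts the opening definition of Post-treatment, which, for a subject who has an Exit challenge, covers only events before that challenge.

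**Step 2. Timed example.** The clock times are assumed for illustration: last randomized dose at 0 h, first half 20–23 h, second half 68–71 h.

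- Gap between halves: 68 − 23 = 45 h, so the condition is met.
- Disputed window: from 23 + 24 = 47 h to 68 h.

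| Onset (h) | Periods whose rule is met |
|---|---|
| 22, 40 | Exit DBPCFC |
| 50, 60 | Post-Exit DBPCFC **and** Post-treatment |
| 69, 90 | Exit DBPCFC |
| 100 (100 − 71 = 29 h after the end) | Post-Exit DBPCFC |

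Only onsets inside the disputed window meet two rules.

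**Step 3. When the window is empty.** If the first half ends at 12:00 and the second starts at 09:00 the next day, the gap is 21 h, under 24 h, and no event can fall in the window. In practice, it opens materially only when the two challenge days are not consecutive.

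**Step 4. Date-only rule.** Let D be the calendar day of the last part of the Exit challenge.

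| Onset date | Period if timed | Period if date only |
|---|---|---|
| D | Exit DBPCFC | Exit DBPCFC |
| D + 1 | Exit DBPCFC if within 24 h, otherwise Post-Exit DBPCFC | Post-treatment |
| D + 2 or later | Post-Exit DBPCFC (necessarily more than 24 h) | Post-treatment |

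From D + 1 onward, the date-only period never matches the timed one. This does not depend on a split challenge. Date-only events on days strictly between the halves are not addressed by either bullet's date-only wording.

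**Step 5. Size.** Inputs from SAP section 4 (planning assumptions, not observed counts): about 50 subjects randomized 1:1, so 25 per arm; 3 or 5 per arm without an Exit challenge, leaving 25 − 3 = 22 or 25 − 5 = 20. Taking all 25 as treated, one affected subject is:

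- Post-treatment row: 1/25 = 4.0%
- Post-Exit DBPCFC row: 1/22 = 4.5%, or 1/20 = 5.0%

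The denominators coincide only if every Safety subject in the arm has an Exit challenge.

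**The case against.** The strongest case on the other side is that this is a copied sentence with little reach. Much of that stands.

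- **The window is narrow.** It is empty unless the halves are more than 24 h apart, and the documents do not say how often that happens. This limits the first conflict but not the date-only one.
- **A reader might infer that adverse event totals are inflated by double counting.** The documents do not support that. The tables count subjects, at most once per period, and the Overall row is separate. A subject may properly appear in several periods, so the rows were never meant to add up. Because SAP 10.3 speaks of classifying events, a programmer may well store one period per event. The likely result is then an undocumented choice between two labels rather than a double count. The text still states both assignments, and the once-per-period rule does not prevent an appearance in two periods.
- **A reader might infer that delayed reactions to the challenge are generally relabelled as post-treatment.** That is too strong. Timed events within 24 h of the challenge's last dose remain in Exit DBPCFC. Under protocol 7.1, in-clinic challenge reactions go on study-specific forms and reach the AE form only if serious, and SAP 10.5 summarises challenge symptoms separately.
- **A date-only fallback is not itself a fault.** Most periods have one. The fault is that this fallback points to a different period from the timed rule it replaces.

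The rest of the SAP suggests an unintended slip. The parallel Screening rule sends between-halves events to one period (Pre-treatment), and the epinephrine analysis in SAP 11.1 uses one combined category for time after treatment or after the Exit challenge.

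**Conclusion.** The two rules conflict as written, and neither a precedence statement nor the addendum resolves them. The consequence is confined to rows of the by-period AE tables and listing: a subject can appear in both Post-Exit DBPCFC and Post-treatment, or in the wrong one, against different denominators. The shift is 4.0% versus 4.5% to 5.0% per affected subject, on the planning assumptions of 25 per arm and 3 to 5 unchallenged. Few events are expected. The Overall row, the overall TEAE summaries (Tables 14.3.1.1 and 14.3.1.7) and every efficacy analysis are untouched. This is an internal contradiction worth correcting, of low severity; it does not show that the safety conclusions would be biased.

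**What to change.** Amend SAP 10.3 before database lock:

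1. Delete the between-halves sentence from the Post-treatment bullet, so that these events belong to Post-Exit DBPCFC only.
2. Move the date-only rule for events from the day after the last part of the Exit challenge out of Post-treatment and into Post-Exit DBPCFC. Apply it also to date-only events on days between the two halves.
3. Keep Post-treatment for events more than 24 h after the last dose, either in subjects with no Exit challenge or before the Exit challenge starts. Its date-only rule for subjects with no Exit challenge can stay.

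One approximation remains. A date-only event on the day after the challenge may have started within 24 h, and a timed record would then place it in Exit DBPCFC. Without a clock time this cannot be settled, so a table footnote should state the convention.

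The cost is a few lines of SAP text and one derivation. Data collection, sample size and trial conduct do not change.
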